**Figure 2. Overview of study objectives and outcome measures**

*CIN: Cervical Intra-epithelial Neoplasia, GP: General Practitioner, HPV: high risk human papillomavirus.*

## **Figure 2 details**

*The purpose of this study is to evaluate the process involved in implementing primary HPV-based cervical cancer screening in primary care. The three primary outcomes are italicised. For full outcome details, including the timepoints at which data are collected, see Table 1 in Additional File 3.*

*\* Data to be presented separately for participants negative for HPV, participants positive for HPV16 and/or 18, and participants positive for HPV other than 16 or 18.*

*\*\* Result options: negative for dysplasia or malignancy, ASC-US (atypical squamous cells of undetermined significance - excluding ASC-US possible high-grade), LSIL (low-grade squamous intraepithelial lesion), ASC-H (atypical cells of undetermined significance, possible high-grade), HSIL (high-grade squamous intraepithelial lesion), cancer (invasive squamous carcinoma of the cervix), adenocarcinoma, cancer other, AGC/AIS (atypical glandular cells / adenocarcinoma-in-situ), or unsatisfactory sample.*

*^ Reasons: requested by General Practitioner due to previous high-grade lesion (test of cure), requested by General Practitioner due to previous abnormal cytology, requested by General Practitioner due to symptoms, requested by General Practitioner for other reason, performed by laboratory due to detection of HPV (not General Practitioner requested), performed by laboratory due to identification of need to test for cure (not General Practitioner requested), or other reason.*

*# The number of patients who have HPV screening will also be presented with the denominator as the number of patients eligible for cervical screening during the study enrolment period, as defined by the reports to primary care organisations as prepared by the NCSP. Non-identifiable demographic data for all patients eligible for screening will be taken from these reports.*

*## Data to be presented separately by whether participants had a cervical or vaginal HPV test.*

---

The full protocol is available on the [ANZCTR trial website](#). Enrolled patients from general practices in New Zealand who are due or overdue for cervical screening were invited to participate. The study aimed to recruit at least 3,000 patients over a six-month period. Study participants could opt for a vaginal HPV self-test or a clinician-taken cervical HPV test. There was no randomisation or blinding. Data were collected throughout the screening pathway.

The study team includes Māori and Pacific steering groups, who were actively involved in the development of the study protocol.

The study was prospectively registered on the [ANZCTR \(ACTRN12622000699763\)](#) on 16/05/2022. The Universal Trial Number is U1111-1276-2570. Ethics approval was granted by the New Zealand Southern Health and Disability Ethics Committee on 1/7/22 (2022 FULL 12546).

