# In some participants a cervical sample for HPV and cytology will be clinically recommended.

---

Objectives	Outcome measures

To describe the impact of HPV testing (by demographics and screening history when numbers permit) in terms of:
 
 
- Proportion of patients screened by each method
 
- Proportion of patients who complete or do not complete each step of the appropriate screening pathway (including uptake of screening, cytology triage, and colposcopy assessment) and referral back to primary care
 
- Screening outcomes in patients with prior abnormalities in relation to transition guideline recommendations
 
- Number of colposcopy referrals, their indication, and outcomes.
 
	
The number (and percentage) of participants that undertook a: vaginal test at home, vaginal test at their general practice without staff assistance, vaginal test at their general practice with staff assistance, cervical test without concurrent cytology, or cervical test with concurrent cytology.g
 
In participants who underwent HPV testing and had an unsatisfactory result, the number (and percentage) that: did have a repeat HPV test or did not have a repeat HPV test.
 
The reason cytology was performed in participants that had cytology results issued from the sample taken during a cervical HPV test. See figure legend for reasons.h
 
The reason cytology was performed in participants that had cytology performed after an HPV test and before colposcopy: positive for HPV result or other reason.*
 
The reason for no cytology report (prior to colposcopy) in participants positive for HPV and had a vaginal HPV test: cytology not considered feasible by the GP, participant declined, participant unable to be contacted, or other.*
 
The number (and percentage) of participants that had a referral for colposcopy by classification of urgency.*
 
In participants referred for colposcopy, the number (and percentage) that received 1, 2, 3 or >3 invitations for an appointment.*

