## **Study appointment**

As outlined in Figure 1, a phone or in-person study appointment took place with a doctor or nurse who was working on behalf of the PHO or was a staff member at a participating general practice. Written or verbal consent was obtained. If verbal consent was obtained, this was formally documented. Demographic information, screening history, and preferred method of contact for results (letter, phone call, or text) were recorded. The participant was asked if they have any symptoms (including abnormal vaginal bleeding, persistent vaginal discharge,

or pain). Participants with relevant symptoms were strongly advised to book an appointment with their doctor or nurse for further review and a cervical HPV test with cytology.

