## **Outcome measures and data management**

The study outcome measures are presented in Figure 2. For further details, see Appendix Table A1.

Staff from participating general practices and PHOs entered data from participants into a secure REDcap database. Study staff also collected:

- Screening data from the NCSP.
- HPV and cytology results from the study laboratory.
- Colposcopy results from hospital records.
- Human papillomavirus vaccination status from the Ministry of Health National Immunisation Register, for participants who specifically consented to have this data collected.
- Socioeconomic status (through coding of street addresses to the New Zealand Index of Deprivation).[15]
- Proximity to health services (through coding of street addresses to Statistics New Zealand's urban accessibility classification[16] and the Geographic Classification of Health).[17]

Participants could opt to withdraw from the study at any time. Data collected up to the point of withdrawal was kept and processed. Data was anonymised prior to analysis.

At the completion of the study, participating general practices and/or PHOs were to provide the total number of their patients identified as being due or overdue for screening during the study period. Deidentified data from patients that did not take part in the study was also collected, including detail on attempts to invite them for screening, demographics, screening history, and whether they had cervical cytology during the study period. For further detail see Appendix Table A1.

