## **Statistical analysis**

Statistical analyses will be performed using R[18] and STATA.[19] Discrete endpoints will be summarised as counts and percentages with 95% binomial confidence intervals (CI). Continuous variables will be displayed graphically, and summarised as means with 95% CI and standard deviations or medians and interquartile ranges as appropriate. Time to event data with censoring will be displayed using Kaplan-Meier or cumulative density plots. Outcomes will be stratified by participants' choice of self-taken vaginal HPV or clinician-taken cervical HPV test and/or other variables of interest such as screening history, age, self-reported ethnicity, socioeconomic status, and region (further details are available in Table A1 of the Appendix).

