**Secondary outcome 35**

Where numbers permit, all outcomes will be presented by:

- Screening history (previously undergone cervical treatment/had an abnormal smear, or not)
- Age band (<25, 25 to 34 years, 35 to 54 years, 55 to 69 years, >69 years)
- Self reported ethnicity (NZ European/Other, Māori, Pacific Island or Asian)
- Socioeconomic deprivation index (Quintiles 1 through to 5)

- Region (Christchurch, Wellington or Whanganui and surrounding areas).
- 

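### Uptake by ethnicity, as written, counts participants on self-report and eligible patients on NCSP reports, so it may be biased in either direction where the two codings disagree

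*Protocol*

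**What the plan says.** **Denominator.** The notes to Figure 2 say the number having HPV screening will also be shown "with the denominator as the number of patients eligible for cervical screening during the study enrolment period", as defined by the NCSP's reports to primary care organisations. They then say: "Non-identifiable demographic data for all patients eligible for screening will be taken from these reports".

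**Classification of participants.** Under Study appointment: "Demographic information, screening history, and preferred method of contact for results (letter, phone call, or text) were recorded". Under Statistical analysis, the stratifiers include "self-reported ethnicity, socioeconomic status, and region". Table A1, Secondary outcome 35, presents all outcomes, where numbers permit, by "Self reported ethnicity (NZ European/Other, Māori, Pacific Island or Asian").

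**Objective.** The objectives in Figure 2 describe the impact of HPV testing "by demographics and screening history when numbers permit", and the pathway steps are listed as "including uptake of screening, cytology triage, and colposcopy assessment".

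**Deprivation.** Under Outcome measures and data management, study staff collect "Socioeconomic status (through coding of street addresses to the New Zealand Index of Deprivation"). That section also lists NCSP screening data, and de-identified practice or PHO data on non-participants that include demographics. It says data were anonymised before analysis.

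**The concern.** A subgroup percentage is sound only if a person is placed in the same subgroup above and below the line. Here the sources named for the two parts differ. A patient who self-reports Māori but is recorded otherwise in the NCSP report would add one to the Māori numerator and one to the non-Māori denominator. Opposite coding errors do the opposite.

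The minority group's denominator is small, so a modest amount of disagreement can move its uptake by several points. The protocol's Background gives inequitable outcomes for Māori and Pacific people as part of the motivation, and its Conclusions hope to identify factors that could reduce inequities. An uptake gap that partly reflects coding would be a poor basis for that advice.

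**Working it through.** **1. The eligible total implied by the protocol.** Sample size gives 266 patients due per practice, 15 practices and 25% declining. Eligible: 15 × 266 = 3,990. Expected participants: 3,990 × 0.75 = 2,992.5, which reproduces the target of 3,000.

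**2. Assumptions for the illustration (none is in the protocol).** Of the 3,990, 600 self-report as the group of interest (15.0%) and 3,390 do not. True uptake is 60% and 75%, so participants number 0.60 × 600 = 360 and 0.75 × 3,390 = 2,542.5. Overall uptake is then 2,902.5/3,990 = 72.7%, slightly below the 75% used in Sample size.

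Let m be the share of the group that the reports record as other, and f the share of others that the reports record as the group.

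**3. Formulas.**

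- Mixed sources, group: 360 / [600(1 − m) + 3,390f]
- Mixed sources, others: 2,542.5 / [3,390(1 − f) + 600m]
- One source (report coding in both parts, coding error unrelated to uptake), group: [360(1 − m) + 2,542.5f] / [600(1 − m) + 3,390f]
- One source, others: [2,542.5(1 − f) + 360m] / [3,390(1 − f) + 600m]

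**4. Results** (gaps in points, from unrounded values; the true gap is 15).

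| m | f | Mixed: group | Mixed: others | Mixed gap | One-source gap |
|---|---|---|---|---|---|
| 0 | 0 | 60.0% | 75.0% | 15.0 | 15.0 |
| 5% | 0 | 360/570 = 63.2% | 2,542.5/3,420 = 74.3% | 11.2 | 14.9 |
| 10% | 0 | 360/540 = 66.7% | 2,542.5/3,450 = 73.7% | 7.0 | 14.7 |
| 15% | 0 | 360/510 = 70.6% | 2,542.5/3,480 = 73.1% | 2.5 | 14.6 |
| 0 | 1% | 360/633.9 = 56.8% | 2,542.5/3,356.1 = 75.8% | 19.0 | 14.2 |
| 0 | 2% | 360/667.8 = 53.9% | 2,542.5/3,322.2 = 76.5% | 22.6 | 13.5 |
| 5% | 1% | 360/603.9 = 59.6% | 2,542.5/3,386.1 = 75.1% | 15.5 | 14.0 |

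Under-recording shrinks the gap, over-recording widens it, and the two can nearly cancel. With one source the gap stays within 1.5 points of the truth in every row. In the last row, where the errors happen to cancel, the mixed figure is the closer one.

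**5. Sensitivity to the assumed inputs.** Hold overall uptake at the protocol's 75% and set a true gap of 10 points. With 10% under-recording and no over-recording, the mixed gap is 2.0, 1.3 or 0.0 points when the group is 8.1%, 15% or 25% of those eligible. (8.1% is the national Pacific share given under Study setting; the other two are assumed.)

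**6. The other denominator available.** Suppose self-reported participants were added to practice-coded non-participants, with m = 10% and f = 0. The group becomes 360/(360 + 240 × 0.90) = 360/576 = 62.5%. Others become 2,542.5/(2,542.5 + 847.5 + 24) = 2,542.5/3,414 = 74.5%. The gap is 12.0: better than 7.0, but still short of 15.

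**The case against.** **The division is not written in one sentence.** It comes from reading the notes to Figure 2, the objectives, Statistical analysis and Secondary outcome 35 together. A same-source numerator is not excluded, since staff already collect NCSP data. This stands as a caution. Still, the protocol names self-report as the ethnicity stratifier for outcomes and the NCSP reports as the source for eligible patients, and never says participants will be re-coded. Following the text leads to the mismatch.

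**It could be left to an analysis plan.** Silence alone would be no finding. Here the protocol states both sources, and they differ.

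**No passage shows that the codings disagree.** This stands. A reader might infer that the gap *is* biased and the inequity masked. The documents do not support that: they do not say how ethnicity in the NCSP reports was obtained, whether it is itself self-reported, or how often it differs. If the codings agree there is no bias, and over-recording would exaggerate the gap.

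**Deprivation.** A reader might infer that deprivation cannot be coded for the eligible population because the data are non-identifiable. A non-identifiable extract can carry an index coded earlier, and the protocol does not list the reports' fields. Only the one-source principle carries over.

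**Importance.** Uptake by ethnicity is not the result on which the study is built. The stated aim is process evaluation, none of the three primary outcomes is uptake by ethnicity, and the breakdown is descriptive and made where numbers permit. This stands and limits the weight of the point.

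**Conclusion.** The point holds in a limited form. As written, uptake by ethnicity over the eligible population draws its numerator and denominator from two ethnicity sources without reconciling them. The gap between groups may therefore be too small, too large or about right, and the plan has no step that would show which.

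The size cannot be known from the protocol. The illustrated range, from 2.5 to 22.6 points for a true 15, rests on an assumed group of 600, assumed uptake of 60% and 75%, and assumed error rates (up to 15% under-recording or 2% over-recording). It shows sensitivity to coding and does not estimate the error in this study. Results whose denominator is participants only are unaffected by this mismatch. This is a cheap improvement to a supplementary breakdown, worth making because equity in uptake is among the matters the study hopes to inform.

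**What to change.** - For every uptake percentage over the eligible population, state that numerator and denominator are classified on the same register field, either the NCSP or the practice record. Obtain that field for participants before the data are anonymised.
- Keep self-reported ethnicity for outcomes whose denominator is participants only.
- Report the cross-table of register against self-reported ethnicity in participants. It shows how far the codings agree among participants, though not among non-participants.
- Apply the one-source rule to deprivation, and show deprivation over the eligible population only if the reports carry an index comparable with the address-coded one.

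**Cost.** One extra field for participants, one table and a sentence or two in the plan. Staff already collect NCSP screening data, although the protocol does not say that an ethnicity field is included. The protocol reports analysis as in progress, so the linkage should be settled promptly. The downside is two ethnicity codings in the report, which need a short explanation. One-source uptake also still carries whatever error the register coding has, a smaller distortion in most of the scenarios above.

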## **Study setting**

The study was performed in three regions of New Zealand: Canterbury, Whanganui, and Wellington. To recruit 3,000 people over six months, it was estimated that 15 general practices would be required to participate.

Compared to the other two regions, Whanganui general practices have a relatively high proportion of Māori enrolled. In view of current inequities in cervical cancer outcomes, and the importance of working with local providers to ensure optimal outcomes for Māori, five

general practice clinics in the Whanganui region were selected following the recommendations of a local steering group which included membership drawn from iwi,\* health, and research providers. The selection of these clinics ensured access to study participation for all six iwi\* in the region.

In the Wellington and Canterbury regions, five general practices in each region were selected for participation using the Microsoft Excel RANDBETWEEN function based on the unique practice identification number. If a selected clinic declined participation in the study, another clinic was randomly selected. If a selected clinic had a small number of enrolled patients, suggesting the study would not reach the recruitment target of 3,000 participants, additional clinics could be randomly selected in the same region.

While general practices in Whanganui have a relatively high proportion of Māori enrolled, the proportion of Pacific patients is comparatively low. To ensure adequate representation of Pacific patients, one practice in each of the Wellington and Canterbury regions was randomly selected from practices that have a comparatively high proportion of Pacific patients enrolled (>8.1%, which is the proportion of the overall New Zealand population that identify as Pacific).[10]

---

\* *Iwi* is the Māori term to describe a kinship group or tribe.

## **Participant inclusion/exclusion criteria**

People were eligible to take part in the study if they were enrolled as a patient in a participating general practice, eligible for cervical screening as part of the NCSP, and due or overdue for a cervical screening test within the study enrolment period.

Patients who were invited to take part in the study could participate within three months of the completion of the six-month recruitment period. Patients were excluded if they were unable or unwilling to provide informed consent.

## **Study recruitment**

The study recruitment process is outlined in Figure 1. Whanganui utilised centralised recruitment through their Primary Health Organisation (PHO), while the Wellington and Canterbury regions recruited directly from the participating general practices. PHOs are regional organisations funded by the New Zealand Ministry of Health to ensure the provision of essential primary health care services (mostly through general practices) to people who are enrolled with the PHO.

Eligible patients were identified using NCSP recall reports, general practice recall registries, and general practice patient information systems. Eligible patients were sent a written invitation (letter or email) and/or text invitation to undergo cervical screening, which included an invitation to opt for HPV testing as part of this study. If a patient did not respond, a second and third invitation could be made by letter, email, text, or direct contact. Patients

could also be recruited when they attend their general practice if they were identified as being due or overdue for cervical screening. In addition to the Participant Information Sheet (Appendix Figure A1), engagement material (such as the study poster and the study engagement brochure (Appendix Figures A2 and A3)) were available to assist in recruitment and/or education. These documents were developed in conjunction with the study Māori and Pacific Steering groups. The Māori engagement brochure was specifically recommended and developed by the Māori steering group. The Pacific steering group subsequently developed the Pacific engagement brochure. The Participant Information Sheet was developed based on materials developed by Te Tātai Hauora o Hine – The National Centre for Women’s Health Research Aotearoa and the findings of New Zealand based studies that specifically investigated acceptability of patient information material about HPV screening.[7, 11] Screening support services could be utilised with other methods of recruitment, as per standard clinical practice for cervical screening in each practice and region.

## **Study appointment**

As outlined in Figure 1, a phone or in-person study appointment took place with a doctor or nurse who was working on behalf of the PHO or was a staff member at a participating general practice. Written or verbal consent was obtained. If verbal consent was obtained, this was formally documented. Demographic information, screening history, and preferred method of contact for results (letter, phone call, or text) were recorded. The participant was asked if they have any symptoms (including abnormal vaginal bleeding, persistent vaginal discharge,

or pain). Participants with relevant symptoms were strongly advised to book an appointment with their doctor or nurse for further review and a cervical HPV test with cytology.

## HPV testing

The advantages and disadvantages of each type of test were discussed with participants.

Participants then selected one of the following:

- Vaginal HPV self-test performed at home or other suitable location.
- Vaginal HPV self-test performed at the general practice with or without support/assistance from a nurse or doctor.
- Clinician-taken cervical HPV test using a cervibroom™ or equivalent.

A clinician-taken cervical HPV test was recommended in people who were symptomatic and people that had a prior high-grade lesion or glandular abnormality and had not returned to three yearly screening (i.e., eligible for a cervical HPV and cytology test, also known as a test of cure). If a cervical HPV sample was recommended, a participant was only offered a vaginal HPV self-test if they declined a cervical test. A nominated requesting clinician was responsible for ordering the HPV test and follow up of the result. A patient could choose not to take part in the study and instead have a conventional cytology test at their general practice or elsewhere.

Participants who opted for a vaginal HPV self-test were given verbal instructions and supplied with a screening kit which included a dry FLOQswabR, sterile container, and written self-test instructions (Appendix Figure A4). If the participant opted to have a vaginal HPV self-test at their general practice, they were provided with a private space to perform the test. They could request a staff member provide assistance or take the sample for them. If the participant opted to have a vaginal HPV self-test at a location other than their general practice (e.g., at home), this ideally would have been performed in conjunction with a telehealth appointment, otherwise participants were provided with contact details to ask for advice or assistance. Participants could send their HPV sample to the study laboratory directly (using a prepaid courier bag) or they could drop it to their general practice.

Clinician-taken cervical HPV tests were taken at the participant's general practice. They were performed under direct visualisation of the cervix by an accredited cervical screener (smear-taker) using a cervibroomTM or equivalent and placed in an LBC medium (Surepath®).

All study samples were sent to an accredited medical laboratory (Canterbury Health Laboratories, Christchurch NZ ), which uses the BD OnclarityTM HPV Assay. This is validated and approved in New Zealand for HPV testing of vaginal swabs for self-testing, as well as for HPV testing of LBC samples. The samples were transported as either a dry FLOQswabR or an LBC vial. Samples were processed as per manufacturer's instructions. The laboratory sent results to the requesting clinician via normal clinical information systems and to the study

[figure not shown]
team. For those LBC samples which included cytology, the results were also directly reported to the NCSP.

